6. PHARMACEUTICAL INFORMATION

6.1 Exemestane (IND# 52662, IND Sponsor: NCI, DCP)

Exemestane is a steroidal, suicide inhibitor of aromatase, the principal enzyme that converts androgens to estrogens. Exemestane is approved for adjuvant treatment of postmenopausal women with estrogen receptor-positive early breast cancer after receiving 2–3 years of prior tamoxifen therapy and for treatment of advanced breast cancer in postmenopausal women whose disease has progressed following tamoxifen therapy. The usual dose is 25 mg once daily after a meal since drug bioavailability is increased 40% with food. Though not approved for breast cancer prevention, exemestane administered to postmenopausal women with a moderately increased risk of breast cancer (≥ 60 years; Gail five-year risk score $>1.66\%$; prior atypical ductal or lobular hyperplasia or lobular carcinoma *in situ*; or ductal carcinoma *in situ* with mastectomy) resulted in a 65% relative risk reduction of invasive breast cancer compared with placebo treatment after three years of follow-up in the MAP.3 trial (3). NCI, DCP is continuing to evaluate exemestane for breast cancer prevention.

Film-coated 25 mg exemestane tablets are provided as white, round, lenticular tablets with uniform appearance and intact edges for once daily oral administration after a meal (Actavis Group PTC ehf, initial United Kingdom (UK) approval in 2010. Full prescribing information is in the summary of product characteristics (SPC) available at: www.medicines.org.uk/emc/medicine/24704). Each tablet contains 25 mg exemestane and the following excipients in its core: povidone K30, maize starch (bleached), starch (partially pregelatinized), sodium starch glycolate type A, cellulose microcrystalline type 101, talc, silica (colloidal anhydrous), magnesium stearate, and polysorbate 80. The tablet film coating contains: partly hydrolyzed polyvinyl alcohol (PVA), titanium dioxide (E171), macrogol 3350, and talc.

Matching placebo tablets are round, lenticular, film-coated tablets containing partially pregelatinized maize starch (Starch 1500), microcrystalline cellulose (Avicel PH102), sodium starch glycolate (Explotab), colloidal silicon dioxide (Aerosil 200), and magnesium stearate (Ligamed MF-2-V). The film coating is Opadry II white, which is PVA based.

Blinded blister packages of study medication (exemestane and placebo tablets) for the three different dosing regimens will be provided: Arm 1) 25 mg exemestane qd (once daily, seven exemestane tablets per week); Arm 2), 25 mg exemestane 3 times a week (three exemestane tablets and four placebo tablets per week); and Arm 3), 25 mg exemestane qw (once weekly, one exemestane tablet and six placebo tablets per week).

6.2 Reported Adverse Events and Potential Risks

According to the UK SPC for 25 mg exemestane film-coated tablets from Actavis UK Ltd., the most commonly reported adverse events (AEs) by early breast cancer patients treated with exemestane were (in order of frequency): hot flushes (22%), arthralgia (18%) and fatigue (16%). AEs similarly or less commonly reported by early breast cancer patients treated with exemestane compared to tamoxifen were headache (14%), insomnia (13%), sweating increased (12%), gynecological disorders (11%), and dizziness (10%). Similar to early breast cancer, in advanced BC hot flushes were the most common AE (14%), followed by nausea (12%). Other common AEs ($\geq 1\%$ to $<10\%$) seen in clinical studies and postmarketing reports were: anorexia, alopecia, carpal tunnel syndrome, constipation, depression, diarrhea, dyspepsia, fracture, osteoporosis, other primary cancer, pain, paresthesia, peripheral edema,

pruritis, reduction in bone mineral density, rash, urticaria, vaginal haemorrhage, visual disturbance, and vomiting. Uncommon AEs ($\geq 0.1\%$ to $< 1\%$) were: acute generalized exanthematous pustulosis, asthenia, gastric ulcer, hepatitis (including cholestatic hepatitis, hepatic enzyme increased, blood bilirubin increased, and blood alkaline phosphatase increased), leucopenia, lymphocyte count decreased, somnolence, thrombocytopenia, and thromboembolism. Though rare, ischemic cardiac events were not significantly different with exemestane compared to tamoxifen (4.5% vs. 4.2%), including individual AEs hypertension (9.9% vs. 8.4%), myocardial infarction (0.6% vs. 0.2%), and cardiac failure (1.1% vs. 0.7%) (Full prescribing information in the SPC is available at: www.medicines.org.uk/emc/medicine/24704).

6.3 Availability

Exemestane and matching placebo tablets in blister packages will be supplied by NCI, DCP.

6.4 Agent Distribution

The European Institute of Oncology will be responsible for the distribution to the Italian sites. Exemestane will only be released by NCI, DCP after documentation of IRB approval of the DCP-approved protocol and consent is provided to DCP and the collection of all Essential Documents is complete (see DCP website for description of Essential Documents).

NCI, DCP-supplied agents may be requested by the Investigator (or their authorized designees) at each Organization. DCP guidelines require that the agent be shipped directly to the institution or site where the agent will be prepared and administered. DCP does not permit the transfer of agents between institutions (unless prior approval from DCP is obtained). DCP does not automatically ship agents; the site must make a request. Agents are requested by completing the DCP Clinical Drug Request form (NIH-986) (to include complete shipping contact information) and faxing or emailing the form to the DCP agent repository contractor:

[name]
MRIGlobal
DCP Repository
[name]
[name]
[contact]
[contact]
Emergency [contact]
Email: [contact]

6.5 Agent Accountability

The Investigator, or a responsible party designated by the Investigator, must maintain a careful record of the inventory and disposition of all agents received from DCP using the NCI Drug Accountability Record Form (DARF) or an institutionally-approved accountability system. The Investigator is required to maintain adequate records of receipt, dispensing and final disposition of study agent. This responsibility has been delegated to the local pharmacist. Include on receipt record from whom the agent was received and to whom study agent was shipped, date, quantity and batch or lot number. On dispensing record, note quantities and dates study agent was dispensed to and returned by each participant.

6.6 Packaging and Labeling

Exemestane and matching placebo tablets for the three dosing arms will be packaged in blinded blister packages and distributed by NCI, DCP or its authorized designee.

Tablets will be packaged in blister card packaging. Each blister card will contain 7 tablets. Participants will receive two wallets of 3 blister cards each (6 blister cards for up to 6 weeks of treatment).

A three-part label will be used for blinding provided by the NCI DCP Repository.

The fixed part of the label will remain attached to the blister cards wallet and will identify the following:

Exemestane 25 mg or Placebo 21 Tablets
Expiration Date: XX-XXXX
Protocol: MDA2014-04-01
Patient ID: _____
Rand #: _____
Dispensed Date: _____

Take one tablet once a day at the same time each day.
Store at Controlled Room temperature 59°F - 77°F (15°C - 25°C)
Keep Out of Reach of Children

Distributed by MRIGlobal for NCI
[name]
[name]

CAUTION: NEW DRUG – LIMITED BY FEDERAL LAW TO INVESTIGATIONAL USE ONLY

The first tear-off portion of the label will be removed from the wallet at the time of dispensing and will be affixed to the Compliance Drug Labels form (Appendix C). This portion of the label will be identical to the first portion of the label, except that it will contain a scratch off area with the unblinding information should the PI need to be unblinded in case of emergency (See Section 6.9).

The second tear-off portion of the label will be removed from the wallet by the pharmacist at the time of dispensing. This portion of the label will contain unblinded information and will be maintained by the pharmacist following institutional guidelines or maybe destroyed if this portion of the label is not needed for drug accountability purposes.

6.7 Storage

Study drug will be stored in a secure location at controlled room temperature, with excursions permitted between 15°-25°C (59°-77°F).

6.8 Registration/Randomization

Screening and Registration into the DMI Database:

Once informed consent has been signed, participants will be registered into the DMI database. The DMI database will assign a participant's PID upon completion of the registration process.

Randomization:

Participants will be assigned a randomization number once the following has been accomplished: eligibility has been verified at the site level, eligibility has been confirmed by the site PI, eligibility CRF has been entered into the DMI web application and the randomization process has been completed by CLO staff. Once eligibility has been verified and confirmed by the CLO staff, the randomization number will be generated by the database and assigned to the participant. Refer to Section 13.2 for details of randomization.

Screening/Registration/Randomization into site-specific databases:

The DMI is the database of record for the study. Registration and randomization should occur per the procedures outlined above. If the site staff need to enter study data into site-specific electronic databases per their institutional requirements, they should do so in accordance with their institutional policies and procedures.

Appropriate CRFs must be completed for any participant who signs an informed consent. If a consented participant is a screen failure and deemed ineligible, the following CRFs must be completed: 1) the Registration CRF; 2) the Randomization CRF with the eligibility box checked "no", 3) the Inclusion and Exclusion CRFs showing why the participant is ineligible, 4) the Off-Study CRF, 5) the Adverse Event CRF, 6) the Concomitant Medication CRF and 7) the Verification CRF. If no Adverse Event and/or Concomitant Medications were assessed by the time the participant is deemed ineligible, the "NONE" box will be checked to complete both CRFs. All participants who sign an informed consent must formally go off study. All participant registration information will be entered into DMI. If a participant experiences a serious adverse event during the screening process, an SAE form must be completed.

6.9 Blinding and Unblinding Methods

- Participants will be blinded to exemestane schedule.
- The Statistician and the Site Study Pharmacist will not be blinded to exemestane schedule.
- All other Investigators will be blinded to exemestane schedule.
- All participants will take 1 tablet per day.
- Study assignments will be unblinded to the Study Investigators and Site Coordinators after all of the data are collected and the study database has been locked. Unblinding will also occur if the participant's physician deems that unblinding is necessary, such as in the case of unacceptable toxicity thought to be related to the study agent or progressive disease.
- The Data and Safety Monitoring Board will also be blinded unless unblinding is warranted (if the participant's physician deems that unblinding is necessary, if the participant becomes pregnant, or after all of the data are collected and the study database has been locked).
- Unblinding will only take place after consultation with the NCI, DCP Task Order Monitor (Medical Monitor). Unblinding will be conducted as follows:

- 1) The Site Investigator contacts the Protocol Principal Investigator and requests the participant's treatment status be unblinded.
- 2) The Protocol Principal Investigator contacts the NCI, DCP Task Order Monitor (Medical Monitor) and requests the participant's treatment status be unblinded. The Protocol Principal Investigator then conveys the Task Order Monitor's decision to the Site Investigator. The Site Investigator then proceeds with unblinding as written out below.

- 3) If the NCI Task Order Monitor cannot be reached and the participant requires emergency care, the Protocol Principal Investigator may authorize the Site Investigator to break the blind.
- 4) If the Site Investigator is unable to reach the Protocol Principal Investigator and the participant requires emergency care, then the Site Investigator must proceed with unblinding as written out below.
- 5) The Site Investigator requests the participant's treatment status be unblinded by the research pharmacist (or designated individual responsible for dispensing drug).
- 6) The Site Investigator officially takes the participant off-study.
- 7) The date and reason for breaking the blind must be submitted by the Site Investigator to the Protocol Principal Investigator, [name], as soon as possible.
- 8) It is the responsibility of the Protocol Principal Investigator to report the date and reason for breaking the blind to the **NCI Medical Monitor, [name]**, via email to [contact], as soon as possible after receiving this information from the Site Investigator.
- 9) The date and reason for breaking the blind must be submitted by the Protocol Principal Investigator to the MD Anderson Consortium Principal Investigator, [name], PhD, or designee as soon as possible via email to [contact] or [contact] or phone at [contact].
- 10) The date and the reason for breaking the blind will be reported by the MD Anderson Consortium Principal Investigator or designee to the MD Anderson DSMB as soon as possible.

6.10 Agent Destruction/Disposal

At the completion of investigation, all unused study agent will be returned to NCI, DCP Repository according to the DCP "Guidelines for AGENT RETURNS" and using the DCP form "Return Drug List".

The guidelines and the form are available on the DCP website.

7. CLINICAL EVALUATIONS AND PROCEDURES

7.1 Schedule of Events

The possibility of taking part in a pre-surgical trial will be presented to incoming postmenopausal women with a highly suspicious palpable lesion or a newly diagnosed ER-positive DCIS or breast cancer. The baseline visit will be scheduled for interested potential participants after histological confirmation.

SCHEDULE OF EVENTS

Evaluation/ Procedure	Screening Visit ¹	Baseline Visit/ Registration (within 14 days prior to randomization)	Randomization	Phone call (Day 1)	Phone call (1 week +3 days prior to surgery) ²	Final Visit (Days 28+1, 35+1, or 42+1) ³	Surgery (Days 29, 36 or 43) ¹²
Screening Informed Consent	X						
Tru-cut biopsy (Eligibility ER + breast cancer)	X						
Informed Consent		X					
Assess eligibility		X					
Medical history		X					
Physical exam/ height/weight/vital signs		X				X ^{9,10}	
Tobacco / alcohol use assessment		X					
Fasting blood lab tests ⁴		X				X	
Blood lab tests that may not be fasting ⁵		X				X ¹⁰	
Fasting blood for biomarkers ⁶		X				X	
Tissue for biomarkers (FFPE blocks or slides)		X					X
Frozen tissue for biomarkers							X
Frozen tissue for proteomics ¹¹							X ¹¹
Concomitant medications		X			X	X	
Baseline symptoms		X					
Confirm eligibility		(X)	X				
Randomization			X				
Dispense study agent ¹³			X ¹³				
Treatment initiation				X ⁷			
Collect study agent						X	X
Compliance					X	X	
Review agent diary/record						X	
Adverse events					X	X	
QoL questionnaire ⁸		X				X	

¹ For the Italian sites only

² If the participant is seen on site for the physical exam and blood safety tests on Day 7 prior to surgery, perform all procedures in person rather than as a phone call. In all other cases call the participant on the phone 1 week +3 days prior to surgery

³ Based on institutional procedure, the final visit may occur on the same day as surgery or the day before. The Final Visit must be

conducted on Days 28+1, 35+1, or 42+1.

⁴ **Fasting** blood lab tests (local lab): Glucose, total cholesterol, HDL cholesterol and triglycerides. Fasting is strongly recommended, but is not mandated. Every effort should be taken to draw these labs fasting.

⁵ Blood tests for safety that do not require fasting: complete blood count (CBC), AST, ALT, Na, K, BUN, total bilirubin, Cl, Ca, alkaline phosphatase, creatinine, and FSH if needed

⁶ **Fasting** blood collection for biomarkers: estradiol, exemestane, 17-dihydroxyexemestane, estrone, estrone-sulphate, androstenedione, testosterone, SHBG, insulin, leptin, adiponectin. Fasting is strongly recommended, but is not mandated. Every effort should be taken to draw these labs fasting.

⁷ The first phone call is not performed if the day of call coincides with the day of the baseline visit

⁸ Quality of Life questionnaire

⁹ Do not repeat the height assessment at the Final Visit. Height measurement will be used from the baseline visit

¹⁰ May be done within 7 days prior to surgery or the day of surgery

¹¹ US Sites Only

¹² Surgery must occur on Days 29, 36 or 43. For this study coordinators are advised to count back from the day of surgery so that participants can either have 28, 35 or 42 days of study agent (ending on the 7th day of blister pack). Study agent can be dispensed in advance of starting agent on Day 1. However, coordinators must remind the participants not to start the study agent until the agent start date is provided to them by the coordinating center, in most cases via a telephone call from the coordinating site to the participant, indicating when to start the agent.

¹³ In person or by mail.

Unresolved AEs with a “possibly”, “probably” or “definitely” attribution to study agent at final visit will be monitored via telephone call at 20-30 days after surgery. AEs occurred after surgery will not be recorded.

7.2 Pre-study Testing at Italian Sites

At the Italian sites, women who wish to consider participating in the trial but have not received a confirmed diagnosis of ER-positive in-situ or invasive breast cancer will require consent for additional evaluations to determine eligibility. Specifically, women who have undergone a histopathologic biopsy diagnosed as in-situ or invasive cancer that has not been stained for ER will be consented to provide access to archival tissue for immunohistochemistry. This may require access to samples from non-study sites. Among women who have not undergone a histopathologic biopsy, consent will be sought to perform core needle biopsies (guided by palpation or imaging) to establish a diagnosis of ER-positive in-situ or invasive cancer.

7.3 Baseline Testing/Pre-study Evaluation

Pre-study evaluation is:

- ER positive (ER \geq 10%) breast cancer histologically confirmed

Baseline exams are:

- **Fasting** blood lab tests that are performed at the local lab (glucose, total cholesterol, HDL cholesterol and triglycerides). Fasting is strongly recommended, but is not mandated. Every effort should be taken to draw these labs fasting.
- Blood lab tests for safety that do not require fasting (complete blood count (CBC), AST, ALT, Na, K, BUN, total bilirubin, Cl, Ca, alkaline phosphatase, creatinine, and FSH if needed)
- Fasting blood sample collection for biomarkers. Fasting is strongly recommended, but is not mandated. Every effort should be taken to draw these labs fasting.

- Physical exam and medical history, vital signs, alcohol and tobacco assessment, anthropometric measurement (height, weight, waist measurement, hip measurement) and quality of life assessment; for the purpose of the present study, minimal requirement for the physical exam visit include the following body/system sites: breasts/ cardiovascular/ gastrointestinal/ lymphnodes

For any participant who is deemed as screen failure, blood samples collected at Baseline are to be destroyed locally at the respective Participating Organization (PO). A Note to File detailing the destruction procedure and associated information is to be generated and documented in the participant's research folder or electronic health record.

At the baseline clinic visit, participants will be instructed on the importance of drug compliance. Participants will be provided and instructed on the use of a pill diary to be completed daily, signed and dated by the participant. Participants will be informed that a pill count will be conducted on their study medication use so that their study medication blisters with remaining tablets must accompany them to the subsequent clinic visit.

Plan the beginning of drug administration according to the day fixed for surgery. Surgery must occur on Days 29, 36 or 43. For this study coordinators are advised to count back from the day of surgery so that participants can either have 28, 35 or 42 days of study agent (ending on the 7th day of blister pack). Study agent can be dispensed in advance of starting agent on Day 1, However, coordinators must remind the participants not to start the study agent until a specific day set for the start of study drug.

7.4 Evaluation During Study Intervention

A phone contact on day one for treatment initiation will occur. If day one is on weekend or holiday the participants will be contacted the previous working day, if randomization and day one coincide, no phone call will be performed.

A phone call a week (+3 days) before surgery to monitor safety and compliance will occur. If the participant is seen on site for the physical exam and non-fasting blood safety tests on Day 7 prior to surgery, perform all procedures in person rather than as a phone call. In all other cases call the participant on the phone 1 week +3 days prior to surgery.

7.5 Evaluation at Completion of Study Intervention

At the final visit, participants will undergo physical exam, vital signs, and anthropometric measurements (weight, waist measurement, hip measurement). These procedures may be done **within 7 days prior to surgery or on the day of surgery**. Do not repeat the height assessment at the Final Visit. Height measurement will be used from the baseline visit.

Blood tests for safety that do not require fasting may be done **within 7 days prior to surgery or on the day of surgery**:

- complete blood count (CBC), AST, ALT, Na, K, BUN, total bilirubin, Cl, Ca, alkaline phosphatase, and creatinine

All other procedures are performed the day of surgery or the day before surgery:

Fasting blood lab tests that are performed at the local lab (glucose, total cholesterol, HDL cholesterol and triglycerides). Fasting is strongly recommended, but is not mandated. Every effort should be taken to draw these labs fasting.

Fasting blood for biomarkers will be collected. Fasting is strongly recommended, but is not mandated. Every effort should be taken to draw these labs fasting.

The date and time of blood draw, the date and time of surgery, and the date and time of last pill intake will be recorded.

The use of concomitant medications, adverse events, compliance, and quality of life assessment will be assessed. Study agent will be collected. A review of agent diary will be performed.

Any kind of surgery will be allowed from simple lumpectomy to total mastectomy. Tissue samples will be collected from the surgical specimen and processed according to Section 10. A detailed Manual of Operations and Procedures will be implemented with the specific procedures for each specimen.

7.6 Post-intervention Follow-up Period

- The follow up visit is a telephone contact to follow up on previously reported unresolved AEs with a “possibly”, “probably” or “definitely” attribution to study agent.
- Only those participants who have reported unresolved AEs with a “possibly”, “probably” or “definitely” attribution to study agent at the previous visit need to be contacted.
- Telephone call should occur at 20-30 days after Surgery. Any AE occurring between surgery and the phone call will not be reported
- The study coordinator will attempt to contact the participant as many times as needed to reach the participant during the “20-30 days after Surgery” window, but a minimum of two attempts must be made. If the coordinator is not able to reach the participant by phone within the study visit window, a protocol deviation is filed.

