2.2 Exemestane

Exemestane is an irreversible aromatase inhibitor. This drug is highly specific and inhibits peripheral conversion of androstenedione to estrogen down to 98%. The drug was recently approved for the adjuvant setting, and the placebo-controlled phase III MAP.3 chemoprevention trial showed an overall 65% reduction in breast cancers and a specific ER-positive breast cancer reduction of 73% in the intervention arm compared to the placebo group (3).

Exemestane is in fact a steroidal aromatase inactivator with a long-lasting effect attributable to a tight covalent binding to the enzyme. The estradiol suppression persists for at least 5 days after administration of a single dose (10). This suggests, especially in a prevention setting, the possibility to reduce the dose and change the time schedule, while still maintaining a significant estradiol reduction. A study of 10 patients found that women who took a daily dose of 10 mg of exemestane achieved equivalent estradiol suppression as women who took a dose of 25 mg daily (11).

The exemestane steroidal structure suggests it may have androgenic properties that could potentially counteract any anti-estrogenic properties in bone and possibly sexual function and menopausal symptoms. The favorable profile on bone may represent an advantage of this agent in prevention settings in unaffected women at increased risk for breast cancer.

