8.4 Off-Study Criteria

Participants may go 'off-study' for the following reasons: the protocol intervention and any protocol-required follow-up period is completed, adverse event/serious adverse event, lost to follow-up, non-compliance, concomitant medication, medical contraindication, withdraw consent, death, determination of ineligibility (including screen failure).

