11. REPORTING ADVERSE EVENTS

DEFINITION: AE means any untoward medical occurrence associated with the use of a drug in humans, whether or not considered drug related. An AE can therefore be any unfavorable and unintended sign, symptom, or disease temporally associated with participation in a study, whether or not related to that participation. This includes all deaths that occur while a participant is on a study.

Please note that all abnormal clinical laboratory values that are determined to be of clinical significance based on a physician's assessment are to be reported as AEs. Those labs determined to be of no clinical significance or of unknown clinical significance (per the physician's assessment) should not be reported as AEs. Any lab value of unknown clinical significance should continue to be investigated/followed-up further for a final determination, if possible.

A list of AEs that have occurred or might occur (Reported Adverse Events and Potential Risks) can be found in §6.2, Pharmaceutical Information, as well as the Investigator Brochure or package insert.

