11.1 Adverse Events

11.1.1 Reportable AEs

All AEs that occur after the informed consent is signed and baseline assessments are completed must be recorded on the AE CRF (paper and/or electronic) whether or not related to study agent.

11.1.2 AE Data Elements:

The following data elements are required for adverse event reporting.

- AE verbatim term
- NCI Common Terminology Criteria for Adverse Events version 4.0 (CTCAE v4.0) AE term (MedDRA lowest level term)
- CTCAE (MedDRA) System Organ Class (SOC)
- Event onset date and event ended date

- Treatment assignment code (TAC) at time of AE onset
- Severity grade
- Attribution to study agent (relatedness)
- Whether or not the event was reported as a serious adverse event (SAE)
- Whether or not the subject dropped due to the event
- Outcome of the event

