11.2.2.6 Follow-up of SAE

Site staff should send follow-up reports as requested when additional information is available. Additional information should be entered on the DCP SAE form in the appropriate format. Follow-up information should be sent to DCP as soon as available. SAEs will be monitored up to 30 days after post-treatment with a visit or a phone call based on the severity of the SAE

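### Sections 7.1 and 7.6 exclude every adverse event starting after surgery, with no exemption for serious events, deaths or agent-attributed events, and so conflict with Section 11

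*Combined protocol and SAP*

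**What the plan says.** All references are to the combined protocol and SAP.

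**The exclusion, stated twice**
- Section 7.6: "Any AE occurring between surgery and the phone call will not be reported".
- Section 7.1, closing note to the schedule: "AEs occurred after surgery will not be recorded".

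**What Section 11 requires**
- Section 11.1.1: "All AEs that occur after the informed consent is signed and baseline assessments are completed must be recorded on the AE CRF", regardless of attribution. It gives no end date and does not refer to surgery.
- Section 11, definition of an AE: "This includes all deaths that occur while a participant is on a study".
- Section 11.2.2: the site reports SAEs within 24 hours of learning of them, with written reports within 48 hours. The postoperative period is not excluded.
- Section 11.2.2.6, under a heading on SAE follow-up: "SAEs will be monitored up to 30 days after post-treatment with a visit or a phone call based on the severity of the SAE".

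**What is kept under either rule**
- AEs are assessed at the telephone contact a week before surgery and at the final visit.
- Sections 7.6 and 11.1.5 follow agent-attributed AEs by telephone to 20 to 30 days after surgery. Section 7.6 limits that call to women whose attributed AE was unresolved at the previous visit.

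**The concern.** Section 1.2 lists safety and toxicity first among the secondary objectives, and Section 2.3 gives a lighter side-effect burden as the reason for testing sparser schedules. Tablets continue until the night before surgery. Section 2.2 says of exemestane: "The estradiol suppression persists for at least 5 days after administration of a single dose". Drug effect can therefore still be present when recording stops.

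The exclusion covers any AE. An SAE is a kind of AE, so on its plain wording the sentence reaches SAEs, deaths and events the investigator judges related to the agent. Section 11 says otherwise. Five sites in two countries (Section 4.4) would have to choose which text to follow, and one of the two choices leaves a possibly drug-related serious event unrecorded.

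**Working it through.** The plan gives no figure on this point to reproduce, so the check sets the two groups of rules against the same events.

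| Event | Sections 7.1 and 7.6 | Section 11 |
|---|---|---|
| Onset between last tablet and surgery | Not excluded | Record (11.1.1) |
| Attributed AE, unresolved at final visit | Followed to 20 to 30 days | Followed to 20 to 30 days (11.1.5) |
| New non-serious AE after surgery, possibly related | Not recorded | Record (11.1.1) |
| New SAE after surgery | Not recorded; no exemption stated | Report within 24 hours of knowledge (11.2.2); 11.2.2.6 unclear on new onset |
| Death after surgery, before a required call | Not recorded; no exemption stated | An AE if on study (Section 11); also an SAE (11.2.1) |

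1. The first two rows agree. The conflict is confined to onset after surgery.
2. The last row depends on when a woman leaves the study. Section 8.4 allows this once "the protocol intervention and any protocol-required follow-up period is completed". A woman with an open attributed AE has a required call at 20 to 30 days, so a death on day 10 after surgery is an on-study death: an AE under Section 11, unreported under 7.6. A woman with no open attributed AE needs no call, and the documents leave her status on day 10 unclear. Her death would still meet the SAE definition in 11.2.1.
3. Section 13.7 starts toxicity evaluability at the first dose and gives no end, so it does not settle the matter.

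**Can the loss be sized?** Inputs: 180 women; 28 to 42 days of treatment; 20 to 30 days from surgery to the call.

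- After surgery: 180 × 20 / 365.25 = 9.9 and 180 × 30 / 365.25 = 14.8 person-years.
- On treatment: 180 × 28 / 365.25 = 13.8 and 180 × 42 / 365.25 = 20.7 person-years.
- Share of the combined window after surgery, lowest: 9.9 / (9.9 + 20.7) = 32%. Highest: 14.8 / (14.8 + 13.8) = 52%. Pairing low with low or high with high gives 42%.
- Counting only five days after surgery for every woman: 180 × 5 / 365.25 = 2.5 person-years, which is 2.5 / (20.7 + 2.5) = 11% to 2.5 / (13.8 + 2.5) = 15% of treatment plus those days.

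Neither calculation measures lost drug-related events. The first treats every postoperative day as drug-attributable. The second uses a lower bound on persistence and applies it equally to all arms, although the schema puts the final biomarker draw 12 hours, 1.5 to 2.5 days and 5.5 to 6.5 days after the last active dose in arms 1, 2 and 3. No postoperative event rate is given.

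**The case against.** The strongest defence is that the cut-off is deliberate. It appears twice in the same sense, and 11.1.1 sets a start and a scope but no end, so 7.6 can be read as supplying the end. Section 11.1.5 fits that reading. Every woman has surgery the morning after her last tablet, and mixing surgical complications into a toxicity comparison would add noise. The 7.6 sentence also sits in a bullet about the timing of a telephone call and does not mention SAEs, while SAE reporting has its own rules in 11.2. A careful site might report a postoperative SAE anyway.

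Much of this stands. Stopping routine collection of ordinary AEs at surgery is a defensible choice, and the documents are contradictory about SAEs; they do not plainly end SAE reporting. But nothing says that 7.6 closes the window in 11.1.1, and that reading still leaves SAEs and on-study deaths unresolved.

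A reader might infer more than the documents support:

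- That all drug-related events after the last dose are lost. Events before surgery are recorded, and unresolved attributed AEs are followed.
- That 11.2.2.6 plainly requires collection of new SAEs to 30 days. It is a follow-up provision. It covers known SAEs and is unclear on new ones.
- That thromboembolism is a delayed risk missed by the cut-off. Section 6.2 lists it as uncommon and says nothing about timing.
- That differing site practice would bias the arm comparison. Randomization is blocked and stratified by center (13.2) and investigators are blinded (6.9), so such bias does not readily follow.

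**Conclusion.** The contradiction is real and should be corrected. It concerns AEs with first onset after surgery, and it matters most for SAEs, deaths and events judged related to the agent. This rests on reading the exclusion literally, since no exemption is written anywhere.

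Its size cannot be given as a number of events. A reader might put it at about 40% of the safety window, but that share runs from 32% to 52% depending on how the ranges are paired, and it assumes that drug risk lasts the whole 20 to 30 days. The documents do not say so.

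The effect is limited to the secondary safety objective, and Section 13.5 treats secondary analyses as exploratory. The primary estradiol comparison and its sample size use no AE data and are unaffected.

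**What to change.** Reconcile Sections 7.1, 7.6, 11 (AE definition), 11.1.1, 11.1.5, 11.2.2 and 11.2.2.6:

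1. State one end date for AE and SAE collection and refer to it in each of these places. The protocol already uses follow-up points at 20 to 30 days after surgery and 30 days after treatment.
2. Narrow the exclusion in 7.1 and 7.6. SAEs, deaths, and AEs judged possibly, probably or definitely related to the agent that come to the site's knowledge up to that date are still recorded and reported.
3. Say in 11.2.2.6 whether SAEs with onset after surgery are covered.
4. Allow events due only to surgery to be flagged and left out of the toxicity comparison.

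The cost is amendment wording and a small amount of extra reporting. Actively questioning all 180 women is not needed. It would cost more, because the existing call reaches only those with an unresolved attributed AE and the others would need a new contact or chart review. The corresponding limitation is that events in women not called are captured only if the site learns of them, and the safety report should say so.
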